3.2 Objectives and related endpoints-phase II

Table 3-2 Objectives and related endpoints-phase II

	Objective	Endpoint
PHASE II		
Primary	Determine the Clinical Benefit Rate (CBR) at 24 weeks amongst patients receiving triple therapy with ribociclib + everolimus + exemestane, for advanced/metastatic HR+, HER2-negative breast cancer following progression on CDK 4/6 inhibitor.	Clinical Benefit Rate (CBR) defined as the proportion of patients with a complete (CR) or partial response (PR), or with stable disease (SD) at 24 weeks as per RECIST 1.1 or Non-CR Non-PD (NCRNPD) at week 24.
Secondary	To determine centrally assessed progression Free Survival (PFS) in HR+ HER2-negative advanced breast cancer.	Progression-free survival (PFS), defined as the time from date of treatment to the date of first documented progression or death due to any cause. If a

Objective	Endpoint
	subject has not had an event, PFS will be censored at the date of last adequate tumor assessment. Disease progression for primary efficacy endpoint derivation will be based on the central radiologist's tumor assessment.
To determine overall response rate (ORR)	Overall response rate (ORR) defined as the proportion of patients whose best overall response is either complete response (CR) or partial response (PR) according to RECIST 1.1.
To determine Overall Survival (OS)	This is defined as the time from treatment initiation with study treatment until death as a result of any cause.
To determine Duration of Overall Response (DOR)	Duration of Overall Response defined as the time between the initial response to the treatment with the combination of ribociclib+everolimus+ exemestane, and subsequent disease progression or recurrence.
To evaluate time to deterioration or ECOG performance status	Time to definitive deterioration of ECOG performance status from baseline.
To determine safety and tolerability	Adverse Events (AEs), serious AE (SAEs), changes in hematology and chemistry values, vital signs, dose interruptions, reductions and dose intensity.
To determine the PK profile of ribociclib and everolimus in the triplet combination	PK parameters including, but not limited to, AUC _{0-4h} , C _{trough} , C _{max} , accumulation ratio (Racc)

4 Study design

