7.1.5 Withdrawal of consent

Patients may voluntarily withdraw consent to participate in the study for any reason at any time. Withdrawal of consent occurs only when a patient:

- Does not want to participate in the study anymore, and
- Does not allow further collection of personal data.

[figure not shown]
In this situation, the investigator should make a reasonable effort (e.g. telephone, e-mail, letter) to understand the primary reason for the patient's decision to withdraw his/her consent and record this information.

Study treatment must be discontinued and no further assessments conducted, and the data that would have been collected at subsequent visits will be considered missing. Further attempts to contact the patient are not allowed unless safety findings require communicating or follow-up.

All efforts should be made to complete the assessments prior to study withdrawal. A final evaluation at the time of the patient's study withdrawal should be made as detailed in the assessment table. Novartis will continue to keep and use collected study information (including any data resulting from the analysis of a patient's samples until their time of withdrawal) according to applicable law.

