7.2 Assessment types

7.2.1 Efficacy assessments

7.2.1.1 Imaging tumor assessments

Tumor response will be assessed locally and centrally according to RECIST Version 1.1 ([Eisenhauer et al 2009](#)). The decision regarding patient management will remain with the local investigator. Patients should have at least one documented measurable lesion (per RECIST v1.1) or in the absence of measurable disease, have at least one lytic or mixed (blastic/lytic) bone lesion at study entry.

Imaging assessments will be performed at screening within 21 days prior to first dose of study treatment and subsequently every 8 weeks (± 1 week) from day one of study treatment during the first 12 months and every 12 weeks (± 2 weeks) thereafter. See [Table 7-2](#) for details of assessments. The 8-week (or 12 week) interval should be respected regardless of whether study treatment is temporarily withheld or modified.

After baseline, selected assessments should be performed on cycle 1 day 1 (will not need to be repeated on day of treatment if performed within 3 days of C1D1) see [Table 7-1](#).

If a patient discontinues treatment for reasons other than radiological documentation of progression of disease, an efficacy assessment should be performed at the time of End of Treatment unless a CT/MRI for tumor measurement was performed within 21 days. Efficacy

assessments should continue as per the scheduled visit per [Table 7-1](#) and [Table 7-2](#), [Table 7-3](#), and [Table 7-4](#).

To the extent possible, each lesion should be assessed using the same imaging method throughout the study.

All patients will undergo CT, PET CT or MRI of the chest, abdomen and pelvis at baseline and subsequent scheduled visits per [Table 7-2](#). The preferred imaging methodology is CT with intravenous (i.v.) contrast. However, if at baseline, a patient is known to have a contraindication to CT i.v. contrast media or develops a contraindication during the trial, a non-contrast CT or PET CT is allowed. MRI plus contrast is allowed, however not recommended of the chest due to respiratory artifacts.

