1.2.1.2.1 End point(s) for secondary objective(s)

The secondary end points for the study are:

- Incidence and severity of adverse events (AE) and serious adverse events (SAE), clinical laboratory values, vital signs and electrocardiogram (ECGs), dose interruptions, reductions and dose intensity.
- PK parameters including, but not limited to, AUC₍₀₋₄₎, C_{trough}, C_{max}, accumulation ratio (Racc).
- Overall response rate (ORR), Disease Control Rate (DCR), Clinical benefit rate (CBR) based on the central assessment as per RECIST v1.1 (CBR is defined as CR, PR, SD or Non-CR-Non-PD (NCRNPD) lasting 24 weeks or longer).

Refer to [Section 3.7.2.1](#) for definitions of ORR, DCR, and CBR. ORR, DCR, and CBR will be assessed based on the responses provided by the Investigator on centrally and locally assessed data.

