3.3.1.4 Adequate tumor response assessment

An adequate tumor response assessment is considered as disease assessment that is indicating any disease status apart from “unknown” or “not done”.

Date of last adequate tumor assessment is the date the last tumor assessment with overall lesion response of CR, PR or SD which was made before an event or a censoring reason occurred. In this case the last tumor evaluation date at that assessment is used. If no post-baseline assessments are available (before an event or a censoring reason occurred) the date of randomization/start of treatment is used.

The tumor assessment will be time slotted using the time windows displayed in Table 3-4:

Table 3-4 Time windows for tumor assessment

| Time window | Planned Visit Timing | Time Window Definition |
|-------------|----------------------|---------------------------------|
| Week 8 | 57 (week 8) | (1,86] days ; (1, 12] weeks |
| Week 16 | 113 (week 16) | (86, 142] days ; (12, 20] weeks |
| Week 24 | 169 (week 24) | (142, 198] days; (20, 28] weeks |
| Week 32 | 225 (week 32) | (198, 282] days; (28, 36] weeks |

| | | |
|---------------------------|---------------|-------------------------------------|
| Week 40 | 280 (week 40) | (282, 352] days; (36, 44] weeks |
| Week 48 | 337 (week 48) | (282, 380] days; (44, 52] weeks |
| Until week 48 (12 months) | X (week Y) | (X-27, X+29] days; (Y-4, Y+4] weeks |
| Week 60 | 421 (week 60) | (380, 464] days; (54, 66] weeks |
| Week 72 | 505 (week 72) | (464, 548] days; (66, 78] weeks |
| Week k (beyond 12 months) | X (week Y) | (X-43, X+41] days; (Y-6, Y+6] weeks |

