3.5.2.2 Phase II

- Clinical Benefit Rate (CBR):

Clinical Benefit Rate (CBR) is defined as the proportion of patients with a complete response (CR), partial response (PR), stable disease (SD) or Non-CR Non-PD (NCRNPD) at 24 weeks as per RECIST V1.1. Thus, any instance of CR, PR, SD or NCRNPD in the first 24 weeks of the treatment, without having an instance of progressive disease (PD) will be accounted for, while calculating CBR. The instances of unconfirmed CR and/or PR will also be accounted for, while calculating CBR.

Demonstration of significant Clinical Benefit Rate (CBR) will be based on this study with at least an 80% power to test the null hypothesis that the clinical benefit rate in 24 weeks is at least 10% or less with an alternative hypothesis that this rate is above 10%.

All the other patients will be counted as not having clinical benefit.

The study is designed to test the following statistical hypothesis:

$$H_0 : \text{CBR} \leq 10\% \text{ vs. } H_1 : \text{CBR} > 10\%$$

The null hypothesis will be rejected and successful clinical benefit will be demonstrated if the lower limit of the 95% confidence interval is greater than at least 0.10. Thus, if 8 or more patients show clinical benefit at 24 weeks then the null hypothesis will be rejected and significant clinical benefit will be demonstrated.

To show significant clinical benefit, currently at least ≥ 8 patients will have to achieve CBR at 24 weeks. But if the number of patients enrolled in the study is higher than the planned number of 33 patients (approximately 44 to 46), then the requirement for the number of patients to have achieved CBR will also increase (up to ≥ 10 patients).

CBR will be summarized by frequency and percentage together with the 95% confidence intervals. An exact binomial confidence interval (implemented using SAS procedure FREQ with EXACT statement for one-way tables) will be calculated [Clopper & Pearson, 1934].

CBR will be calculated based on FAS; however, patients with only non-measurable disease at baseline will be included in the numerator if they achieved a complete response.

For primary efficacy variable, the analysis time point is when all patients who are enrolled complete 24 weeks or discontinue from the study earlier. Phase 1 patients who had received the RP2D and are post CDK 4/6 completing 24 weeks or discontinue early will also be included in the final phase II analysis.

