3.5.3 Handling of missing values/censoring/discontinuations

Not Applicable.

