3.15 Interim analysis

No formal interim analysis is planned. One interim statistical analysis will be done after completing Phase I part of the study. The final analysis will be after completing Phase II of the study.

4 Sample size calculation

Phase I: In the phase I of the study, there will be 3-6 patients per dose level cohort (for a total of 3 cohorts). A RP2D will be based on safety profile of the dose escalation (cohort A&B) and the dose de-escalation (cohort C). RP2D will be defined as the optimal dose level at which 33%

or less experience DLTs. Thus, including confirmation, at least 3-6 patients will be required for Phase I for each cohort.

Phase II: The sample size is based on an exact test for single proportion to test the null hypothesis $H_0: p \leq 0.10$ where p is the clinical benefit rate in 24 weeks. If the true rate is $p \geq 30\%$, then with one-sided alpha level of 0.05% and a power of 80%, a minimum of approximately 60 (30 per group) evaluable patients are required for the study.

Including dropout rate of 10%, to get 60 evaluable patients, a total of approximately 66 patients (33 patients per group) will be enrolled for the phase 2 of the study for each group (group 1 and group 2). Thus, if fewer than 8 patients show clinical benefit at 24 weeks out of 33 patients within each group then the study will not show significant clinical benefit. Thus, approximately at least 66 patients (33 patients per group (group 1&2)) will be required to be enrolled for the Phase II of the study.

So far 46 patients for group 1 and 33 patients for group 2 are recruited for phase 2.

5 Change to protocol specified analyses

None

6 Appendix

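### The SAP's working rule for the primary endpoint credits one early non-progression scan as clinical benefit, which contradicts the 24-week status that the SAP and protocol define

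*SAP*

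**What the plan says.** Protocol Table 3-2 defines the Phase II primary endpoint as the proportion with CR or PR, "or with stable disease (SD) at 24 weeks as per RECIST 1.1 or Non-CR Non-PD (NCRNPD) at week 24".

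SAP 3.5.2.2 opens with the same timing. The next sentence turns it into a counting rule: "any instance of CR, PR, SD or NCRNPD in the first 24 weeks of the treatment, without having an instance of progressive disease (PD") is to be counted. The rest of that section places all remaining patients in the no-benefit category and says that a best overall response of UNK is not a success. SAP 3.7.2.1 repeats the counting rule for Phase I, although SAP 1.2.1.2.1 says of Phase I that "CBR is defined as CR, PR, SD or Non-CR-Non-PD (NCRNPD) lasting 24 weeks or longer".

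SAP 3.5.3, headed "Handling of missing values/censoring/discontinuations", is the place for missing data in the primary analysis. It is marked not applicable. SAP Section 5 lists no changes from the protocol's analyses.

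SAP Table 3-4 does define a Week 24 slot, "169 (week 24) | (142, 198] days; (20, 28] weeks", but the CBR rule does not refer to it.

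**The concern.** A definition tied to 24 weeks and a rule that accepts any earlier non-progression scan give different answers for one type of patient: an early SD or NCRNPD, no recorded progression, and no assessment at or after Week 24. The definition cannot count that patient as a success; the working rule must. A programmer would probably code the working rule, because it is the more specific text.

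For these patients the error runs in one direction, towards success. There is no control arm in which the same error could cancel, the study is open-label, and each group is judged alone against 10%. Two analysts following SAP 3.5.2.2 in good faith could report different primary results from the same data.

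**Working it through.** **1. One patient taken through every rule.** Scan on Day 57 (the planned Week 8 day in SAP Table 3-4) shows SD. Consent is withdrawn on Day 70.

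- Later scans: Protocol 7.1.5 then requires "no further assessments conducted, and the data that would have been collected at subsequent visits will be considered missing". No progression can be recorded after Day 70.
- End-of-treatment scan: not required, because the last scan was 70 − 57 = 13 days earlier, inside the 21-day waiver in Protocol 7.2.1.1.
- Protocol Table 3-2 and the opening of SAP 3.5.2.2: SD at 24 weeks is not shown, so no benefit.
- SAP counting sentence: one SD within 24 weeks and no PD, so benefit.
- UNK rule: SAP 3.3.1.6 assigns SD after a single SD more than 6 weeks (42 days) from start. Day 57 qualifies, so best overall response is SD and the UNK rule does not apply.
- Non-responder rule in SAP 3.3.1.3: it treats SD itself as non-response, so it serves ORR and cannot govern CBR.
- Catch-all for remaining patients: it reaches only those who fail the counting sentence.
- SAP 3.5.3: silent.

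The patient is counted as a success. Loss to follow-up after the same scan gives the same result. So, on the literal wording, does death before Week 24 without documented progression, because the sentence names only PD.

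**2. The plan's decision rule.** Inputs: null rate 0.10 and alternative 0.30 (SAP Section 4); success if the exact 95% lower limit exceeds 0.10, stated as at least 8 benefits, rising to 10 at about 44 to 46 patients (SAP 3.5.2.2); 33 patients recruited in Group 2 and 46 in Group 1 (SAP Section 4).

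Clopper-Pearson lower limit for r of n: the 0.025 quantile of Beta(r, n − r + 1).

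| r/n | Lower limit | Result |
|---|---|---|
| 7/33 | 0.090 | fail |
| 8/33 | 0.111 | pass |
| 9/46 | 0.094 | fail |
| 10/46 | 0.109 | pass |

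The stated rule reproduces. Its exact one-sided error is P(X ≥ 8; n=33, p=0.10) = 1.4%, with power 81.8% at p=0.30. For 10 of 46 the figures are 1.4% and 92.0%.

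One credited patient adds 1/33 = 3.0 percentage points to the observed rate in Group 2 and 1/46 = 2.2 in Group 1.

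**3. Illustration of the effect.** Suppose k patients are credited only through the counting sentence, and each of the other n − k has a true 24-week benefit probability of 0.10. The chance of success is P(X ≥ r − k), with X binomial (n − k, 0.10).

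| k | n=33, r=8 | n=46, r=10 |
|---|---|---|
| 0 | 1.4% | 1.4% |
| 1 | 3.6% | 3.2% |
| 2 | 8.3% | 6.8% |

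The confidence-interval rule implies a one-sided level of 2.5%. One credited patient exceeds that but stays below 5%; two exceed 5%.

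**4. Limit on the denominators.** Protocol 10.5.1 and SAP 3.5.2.2 add to the final analysis Phase I patients who were treated at the recommended dose after a CDK4/6 inhibitor. The true denominators will therefore be somewhat larger than 33 and 46 if any qualify, and the cut-offs may move: the lower limit is 0.098 for both 8/37 and 10/51, so neither would pass. The tables above describe the recruitment counts only.

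**The case against.** The strongest reply is that the SAP keeps the right endpoint. It ties CBR to Week 24 in 1.2.2.1.1, 3.5.1.2 and several sentences of 3.5.2.2, so the counting sentence could be read as loose drafting. This stands in part. A reader might infer that the SAP simply replaced the protocol endpoint, and the text does not support that: SAP 3.5.2.2 contradicts itself. The contradiction still has to be resolved before programming.

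The second reply is that few patients will fall in the gap. Scans continue every 8 weeks after stopping for reasons other than progression (Protocol 4.1.3 and 7.1.7). At the end of treatment "an efficacy assessment should be performed at the time of End of Treatment unless a CT/MRI for tumor measurement was performed within 21 days". Protocol 7.1.5 also asks for a last evaluation when consent is withdrawn. This stands: these provisions reduce the number. They do not establish status at Week 24 for patients who withdraw, are lost or die.

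Three stronger readings are tempting and should not be adopted.

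- *The rule can only raise the observed CBR.* Table 3-2 can be read as attaching the 24-week timing only to SD and NCRNPD. On that reading a PR at Week 8 followed by PD at Week 16 counts under the protocol but not under the SAP, which excludes any PD.
- *The planned 10% dropout gives the number of miscounted patients.* That allowance covers patients who are not evaluable, a term left undefined. Those with no post-baseline scan would be UNK and are already not successes.
- *The 30-day cut-off on off-treatment scans makes this worse.* SAP 3.3.1.6 states that cut-off for best overall response; on its wording it does not reach CBR.

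**Conclusion.** The concern holds as an internal contradiction in the primary endpoint definition. Followed as written, the counting sentence credits patients whose 24-week benefit is unknown, or who died without documented progression, and nothing else in the SAP corrects this. The conflict with the protocol is clear for SD and NCRNPD and arguable for CR and PR.

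Its size cannot be fixed in advance, because the documents give no number for such patients. What can be said is that one patient separates pass from fail at the recruited sizes, and that one or two credited patients would raise the 1.4% chance of a false success to between 3.2% and 8.3%. Those percentages assume exactly k credited patients, a true rate of 10% in the rest, and no added Phase I patients. They are an illustration and not an estimate of the trial's error rate. The point should be corrected before the primary analysis is programmed.

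**What to change.** In SAP 3.5.2.2, and in the matching Phase I text in 3.7.2.1, replace the counting sentence with: clinical benefit requires CR, PR, SD or NCRNPD on an assessment in the Table 3-4 Week 24 window (Days 143 to 198), or on a later assessment if the Week 24 scan was missed, with no earlier PD or death.

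In SAP 3.5.3, replace the present entry with: all other patients in the FAS, including those with no assessment at or after the Week 24 window, count as no clinical benefit.

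Report how many patients in each group lack a Week 24 scan, and add a sensitivity analysis that requires a scan inside the window.

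The cost is a few sentences in the SAP. No new data are needed, because the scans are already scheduled on and off treatment. The observed CBR may be slightly lower. Accepting a later scan protects a patient who missed Week 24 but was still free of progression at the next visit.

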	
A minimum of approximately 60 evaluable patients (30 per group (group 1, and group 2) are required for Phase II of this study to evaluate clinical benefit rate at 24 weeks.
 
The sample size is based on an exact test for single proportion to test the null hypothesis $H_0: p \leq 0.10$, where p is the clinical benefit rate in 24 weeks. If the true rate is $p \geq 30\%$, then with one-sided alpha level of 0.05% and a power of 80%, a minimum of approximately 30 evaluable patients for each group are required for the study. Including dropout rate of 10%, to get at least 30 evaluable patients, a total of approximately 33 patients for each group (group 1 and group 2) will be enrolled.
 
If 8 or more patients show clinical benefit at 24 weeks then the null hypothesis will be rejected and significant clinical benefit will be demonstrated. (See Section 10)
 
Details of the statistical analysis and data reporting will be provided in the RAP.

--	---

1 Background

[figure not shown]

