A minimum of approximately 60 evaluable patients (30 per group(Group 1 and Group 2)) are required for Phase II of this study to evaluate clinical benefit rate at 24 weeks.

In each phase II group (1 and 2), if 8 or more patients show clinical benefit at 24 weeks then the null hypothesis will be rejected and the study will demonstrate significant clinical benefit.

RP2D:

[figure not shown]
Following completion of the phase I, dose escalation portion of this trial, it was determined that the RP2D to be explored in group 1 of phase II is as follows:

300mg ribociclib (daily) + 2.5mg everolimus (daily) + 25mg exemestane (daily)

RP2D for group 2 of phase II was determined after completion of cohort C, of phase I, as follows:

200mg ribociclib (daily) + 5mg everolimus (daily) + 25mg exemestane (daily) During Phase II, all patients must have progressed on any CDK 4/6 inhibitor. Prior CDK 4/6 inhibitor will be defined as disease progression while on, or within one month of discontinuing any CDK 4/6 inhibitor (i.e. palbociclib, ribociclib, or abemaciclib).

Figure 4-1 Study design

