10.4.2 Sample size and accrual

Phase I: In the phase I of the study, there will be 3-6 patients per dose level cohort (for a total of 3 cohorts). A RP2D will be based on safety profile of the dose escalation (cohort A&B) and the dose de-escalation (cohort C). RP2D will be defined as the optimal dose level at which 33% or less experience DLTs. Thus, including confirmation, at least 3-6 patients will be required for Phase I for each cohort.

Phase II:

The sample size is based on an exact test for single proportion to test the null hypothesis $H_0: p \leq 0.10$ where p is the clinical benefit rate in 24 weeks. If the true rate is $p \geq 30\%$, then with one-sided alpha level of 0.05% and a power of 80%, a minimum of approximately 60 (30 per group) evaluable patients are required for the study.

Including drop out rate of 10%, to get 60 evaluable patients, a total of approximately 66 patients (33 patients per group) will be enrolled for the phase 2 of the study for each group (group 1 and group 2). Thus, if fewer than 8 patients show clinical benefit at 24 weeks out of 33 patients within each group then the study will not show significant clinical benefit. Thus, approximately at least 66 patients (33 patients per group (group 1&2)) will be required to be enrolled for the Phase II of the study

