Phase II: This is a multi-center open label study to evaluate the antitumor activity of the ribociclib (LEE011) +everolimus + exemestane combination in patients with advanced/metastatic HR+, HER2 negative breast cancer that have progressed on CDK4/6 inhibitor based therapy. This part of the study will be continued after the MTD/RP2D is determined in the Phase I.

A minimum of approximately 60 evaluable patients (30 per group (Group 1 and Group 2)) are required for Phase II of this study to evaluate clinical benefit rate at 24 weeks.

In each phase II group (1 and 2), if 8 or more patients show clinical benefit at 24 weeks then the null hypothesis will be rejected and the study will demonstrate significant clinical benefit.

RP2D:

Following completion of the phase I, dose escalation portion of this trial, it was determined that the RP2D to be explored in Group 1 and Group 2 of phase II are as follows:

[figure not shown]
Group1: Ribociclib (300 mg daily) + everolimus (2.5 mg daily) + exemestane (25 mg daily).

Group 2: Ribociclib (200 mg daily), everolimus (5 mg daily) and exemestane (25 mg daily)

During Phase II, all patients must have progressed on any CDK 4/6 inhibitor. Prior CDK 4/6 inhibitor will be defined as disease progression while on, or within one month of discontinuing any CDK 4/6 inhibitor (i.e. palbociclib, ribociclib, or abemaciclib).

To show significant clinical benefit, currently atleast ≥ 8 patients will have to achieve CBR at 24 weeks. But if number of patients enrolled in study is higher than the planned number of 33 patients (approximately 44 to 46), then the requirement for number of patients to have achieved significant clinical benefit will also increase (upto ≥ 10 patients).

Figure 1-1 Study Design

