6.4 Statistical models

6.4.1 Analysis of Response Rate

Patients with clinical benefit, disease control and responders are summarized in terms of percentage rate with 95% confidence interval. An exact binomial confidence interval (implemented using the SAS procedure FREQ with the EXACT statement for one-way tables) is calculated ([Clopper & Pearson, 1934](#)).

The SAS procedure FREQ was used with the following code:

PROC FREQ DATA=*dataset*;

BY *treatment*;

TABLES *response* / binomial;

EXACT binomial;
RUN;

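### The protocol's fixed count of 8 per Phase II group matches its exact 95% CI rule only for 30 to 36 patients; Group 1 has 46 and needs 10, which the SAP largely, but loosely, corrects

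*SAP*

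**What the plan says.** Protocol 10.5.1 and SAP 3.5.2.2 state the criterion in the same terms: "The null hypothesis will be rejected and successful clinical benefit will be demonstrated if the lower limit of the 95% confidence interval" exceeds 0.10. The interval is the exact Clopper-Pearson interval, and SAP 6.4.1 confirms the method: "An exact binomial confidence interval (implemented using the SAS procedure FREQ with the EXACT statement for one-way tables) is calculated". Both sections then present a count as the consequence: "Thus, if 8 or more patients show clinical benefit at 24 weeks then the null hypothesis will be rejected".

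The protocol prints that count elsewhere with no sample size attached. The synopsis has "If 8 or more patients show clinical benefit at 24 weeks then the null hypothesis will be rejected and significant clinical benefit", and section 4.1 applies it group by group: "In each phase II group (1 and 2), if 8 or more patients show clinical benefit at 24 weeks then the null hypothesis". Only section 10.4.2 ties it to the planned size: "Thus, if fewer than 8 patients show clinical benefit at 24 weeks out of 33 patients within each group".

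The SAP adds a clause that the protocol lacks. Section 3.5.2.2 reads "But if the number of patients enrolled in the study is higher than the planned number of 33 patients (approximately 44 to 46", and section 1.1, in parallel wording, continues "then the requirement for number of patients to have achieved significant clinical benefit will also increase"; both then cap the increase at a requirement of 10 or more. SAP section 4 reports 46 patients recruited to Group 1 and 33 to Group 2. The total of 79 agrees with the Phase II enrolment in the protocol's Amendment 3 rationale. Section 4 repeats 8 out of 33 and gives no count for 46.

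The primary analysis uses the FAS, that is, patients who took at least one dose of each of the three drugs (SAP 2.2.1). Phase I patients who received the RP2D after a CDK4/6 inhibitor are added to the final Phase II analysis (protocol 10.5.1, SAP 3.5.2.2). Their number is not stated.

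**The concern.** A fixed count and a confidence-limit rule agree only over a narrow range of n. As n grows, the same count is a smaller proportion, its lower limit falls, and the chance of reaching it under the null rises. Group 1 is 13 patients above its planned 33, yet the protocol's count has not moved. For some Group 1 results the protocol therefore gives two answers to the primary question, and the answer chosen could depend on which sentence is read after the data are known. The study is open-label and each group has no concurrent control, so this threshold is all that separates a positive group from a negative one.

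**Working it through.** **Inputs.** Null rate 0.10 and design alternative 0.30 (protocol 10.4.2, SAP 4). Two-sided 95% exact interval, lower limit to exceed 0.10 (protocol 10.5.1, SAP 3.5.2.2). Planned 30 evaluable and 33 enrolled per group (protocol 10.4.2). Actual 46 and 33 (SAP 4).

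**Formulas.** For x benefits in n patients, the Clopper-Pearson lower limit L is the 2.5% quantile of Beta(x, n − x + 1). L exceeds 0.10 exactly when P(X ≥ x | n, 0.10) is below 0.025. That tail probability is also the type I error of requiring x. Power is P(X ≥ x | n, 0.30).

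**Step 1: reproduce the plan's count.**

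| n | x | Lower limit | Exceeds 0.10? |
|---|---|---|---|
| 30 | 7 | 0.0993 | no |
| 30 | 8 | 0.1228 | yes |
| 33 | 7 | 0.0898 | no |
| 33 | 8 | 0.1109 | yes |

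Eight is correct at both planned sizes.

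**Step 2: find how far each count holds.**

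| Count | Last n that passes (limit) | Next n (limit) |
|---|---|---|
| 8 | 36 (0.1012) | 37 (0.0983) |
| 9 | 43 (0.1004) | 44 (0.0980) |
| 10 | 50 (0.1003) | 51 (0.0982) |

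The smallest sufficient count is therefore 8 for n = 30–36, 9 for 37–43, 10 for 44–50 and, continuing the same search, 11 for 51–57.

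**Step 3: Group 1 at n = 46.**

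| Count | Lower limit | CI rule | Protocol count | Type I error at 0.10 | Power at 0.30 |
|---|---|---|---|---|---|
| 8 | 0.0782 | fails | passes | 8.4% | 98.3% |
| 9 | 0.0936 | fails | passes | 3.6% | 96.1% |
| 10 | 0.1095 | passes | passes | 1.4% | 92.1% |

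The protocol's two statements disagree at exactly 8 or 9 of 46. The probability of landing there is 0.0840 − 0.0140 = 0.070 if the true rate is 10%, and 0.9830 − 0.9205 = 0.0625 if it is 30%.

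**Step 4: check the SAP's clause.** It pairs about 44 to 46 patients with 10. The limits for 10/44, 10/45 and 10/46 are 0.1147, 0.1120 and 0.1095, and the limits for 9 are 0.0980, 0.0958 and 0.0936. Ten is exactly the CI-rule count throughout that range.

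**Step 5: sensitivity to Phase I additions (number unknown).** Starting from 46, Group 1 stays at 10 with up to 4 additions (n = 50) and needs 11 from 5 (n = 51). Starting from 33, Group 2 stays at 8 with up to 3 additions (n = 36) and needs 9 from 4 (n = 37).

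**The case against.** The strongest reply is that the CI sentence comes first and the count is introduced only as its consequence, so the CI already governs. It is computed on the patients actually analysed, adjusts by itself, and makes any printed count illustrative. Protocol 10.4.2 ties 8 to 33 patients, and the SAP raises the count to the right number for 44 to 46. On this view only an editorial tidy-up is left.

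Much of that stands for the SAP. A reader might infer from the capped wording of the increase that the SAP would accept 9/46. It does not: the CI sentence in the same section excludes it, since the lower limit is 0.0936. A reader might also argue for 9 by taking the sample-size text's one-sided 0.05% to mean one-sided 5%, because P(X ≥ 9 | 46, 0.10) = 0.0364. That requires altering the printed figure, and SAP 2.1 sets two-sided 0.05 tests and 95% intervals as the default, which supports 10. The alpha statement is a separate matter.

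It is likewise tempting to say that the Phase I additions make 8 and 10 wrong. The documents do not give their number, and it may be near zero because Phase I did not require prior CDK4/6 exposure (protocol 5.1).

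The reply does not dispose of the protocol. The synopsis and section 4.1 state the 8 as a rejection rule in its own right, with no n and no CI beside it, and section 4.1 applies it to each group. At 46 that rule is wrong by the protocol's own criterion.

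**Conclusion.** The point holds for the protocol, and in a narrower form for the SAP. In the protocol, the unscaled 8 contradicts the CI rule at Group 1's recruited size: two outcomes, 8/46 and 9/46, would be called successes by the count and failures by the interval, and a rule of 8 or more would carry 8.4% type I error. In the SAP the number for 44 to 46 is right. What is left is that three statements stand together without an order of precedence, that the increase is worded as a ceiling, and that its trigger is patients enrolled rather than patients analysed.

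The documents do not support saying that the trial will be judged at 8.4% type I error, because the SAP expressly raises the count. The Group 1 figures assume 46 patients in the FAS and no Phase I additions; 10 remains the required count anywhere from 44 to 50. This should be fixed because it is the primary success criterion, but it calls for clarification rather than redesign.

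**What to change.** State in SAP 1.1, 3.5.2.2 and 4 that the sole success criterion in each group is an exact two-sided 95% Clopper-Pearson lower limit above 0.10, computed at that group's final FAS n. Replace the fixed 8 and the capped increase with counts marked as illustrative:

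| Analysed n | Count needed |
|---|---|
| 30–36 | 8 |
| 37–43 | 9 |
| 44–50 | 10 |
| 51–57 | 11 |

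Make the same change in the protocol synopsis, 4.1, 10.4.2 and 10.5.1 at the next amendment. Protocol 12.1 requires written amendment and approval, so the SAP clarification should come first. Because the criterion follows the analysed n, it also covers any Phase I patients added and any recruited patients who fall outside the FAS.

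The cost is wording only: no new data and no change to the planned interval. The one real consequence is a stricter count in Group 1 than the protocol prints, 10 instead of 8 at n = 46. Power at a true rate of 30% falls from 98.3% to 92.1%, still above the planned 80%.
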